The dosage escalation medication regimen in this protocol is similar to those studies conducted for smoking cessation and for ataxia. The active medication will be dosed twice daily (1 mg BID) due to convention, though the half-life of the drug is listed as 24 hours. A week of dose escalation will allow for maximal tolerability. The worsening of neuropsychiatric symptoms reported in some patients with other disorders on varenicline appears to be isolated in patients with prior psychiatric conditions, but this has not always been the case. In order to monitor for this potential side effect and to screen for potential sub-clinical depression, the Beck Depression Inventory will be given to all subjects and followed during the course of the study. Suicidal ideation and attempt has also been reported in patients taking varenicline, so the Beck Scale for Suicidal Ideation will also be administered to participants during the course of the study. There are no aspects of the proposed dosing schedule that are not FDA-approved for other indications. This study is

of high priority due to the absence of any proven medications to treat imbalance in this disorder.

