#### **MANAGEMENT OF ADVERSE EXPERIENCES**

The four most common adverse events with varenicline in adult studies are nausea, insomnia, abnormal dreams, and headache. Other side-effects include: constipation, dry mouth, flatulence, and dizziness. Psychiatric side effects have been reported and will be strictly monitored. The four most common placebo side-effects also include: nausea, insomnia, abnormal dreams, and headache. Adverse events will be documented on the adverse event form and sent to the independent medical monitor.

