#### **STATISTICAL CONSIDERATIONS**

### General Design Issues

The primary and secondary outcomes will be analyzed using SPSS. The independent medical monitor will review adverse event data and the final analysis. There will be no interim analysis performed. The independent medical monitor will not be blinded to treatment arm. There will be no stratification.

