### Outcomes and Data Analysis

- Primary outcome (Aim 1): The primary hypothesis will be tested using a paired *t*-test using means of the total Berg Balance Scale score before and after treatment. Linear regression will be used to determine if there is an association among outcome, gender, age, race, or ethnicity. This outcome will be determined by the rating of patients from a blinded movement disorders neurologist.
- Secondary outcomes (Aim 2): Secondary hypotheses will be tested using paired *t*-tests on the full MDS-UPDRS, the TUG, and the ABC scale. For side effect analysis, logistic regression will be performed with the treatment arm as the dichotomous outcome and the MMSE and FAB as covariates. In addition, gender and age will also be included as covariates.
- Side effects (Aim 3): Adverse events will be recorded and classified as to seriousness of the side effect and likelihood that the side effect is related to the drug. Adverse events in the treated group versus the untreated group will be compared and any events that are significantly more frequent in the treated group will be identified.
- Sample Size and Accrual: Sample size was estimated using published means and standard deviations of the BBS in PD subjects. The mean of the rating scale is 40.22 with a standard deviation of 8.48. Based on a published effect size of a change of 8 points, and using a power of 0.80 and a significance of 0.05 with a two sided test, a sample size of 19 subjects for each group would be needed for a parallel design. To allow for attrition, 42 subjects will be recruited. Intent to treat analysis will be performed. The number of subjects lost to follow-up is likely to be low due to the relative lack of efficacy of other forms of treatment for this particular symptom of PD. Power for calculating secondary outcomes is lower than 0.8.

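### Aim 3 identifies adverse events only by an unspecified significance test, which suits small safety imbalances poorly in a 42-subject trial

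*Combined protocol and SAP*

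**What the plan says.** Under Outcomes and Data Analysis, the side-effects item (Aim 3) has three steps. Each adverse event is recorded and classified by seriousness and by likely relation to the drug. Next, "Adverse events in the treated group versus the untreated group will be compared". Finally, "any events that are significantly more frequent in the treated group will be identified". For this comparison the protocol gives no test, significance level, sidedness, effect estimate or confidence interval.

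The trial is sized on the Berg Balance Scale alone: 19 per group, 42 recruited. The same section concedes that "Power for calculating secondary outcomes is lower than 0.8" but says nothing about the power of the adverse-event comparison.

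The protocol treats psychiatric effects as a particular concern. Management of Adverse Experiences states "Psychiatric side effects have been reported and will be strictly monitored", and the Rationale adds that "the Beck Scale for Suicidal Ideation will also be administered to participants during the course of the study". General Design Issues states "The independent medical monitor will review adverse event data and the final analysis". That monitor is not blinded to arm. Data Monitoring rules out an interim safety analysis.

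**The concern.** A significance rule works for large excesses of common events. With about 21 subjects per arm it does little for uncommon ones, and neuropsychiatric events may be of that kind. Because the test is not named, whether a small imbalance is identified depends on a choice that could be made after the data are seen. And because no estimate or interval is promised, the final report could state that an event was not significantly more frequent without showing how large an excess the data still allow.

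**Working it through.** **Inputs.** 42 randomized (Interventions, Administration, and Duration). The allocation ratio is not stated. The sample-size item counts subjects for each of two groups, so 1:1 and 42/2 = 21 per arm are assumed. The two-sided 0.05 level is stated only for the sample-size calculation and is carried over to Aim 3 as an assumption. All event rates below are assumptions.

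**The plan's own figure.** With a difference of 8 and SD 8.48, the normal approximation gives n = 2(1.960 + 0.842)² × 8.48² / 8² = 17.6, so 18 per arm. The two-sample t calculation gives 18.65, so 19 per arm, with power 0.808. The stated 19 per group reproduces. It concerns the Berg Balance Scale and says nothing about adverse events.

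**3 of 21 v 0 of 21.**
- Fisher, two-sided: 2 × C(21,3)/C(42,3) = 2 × 1330/11480 = 0.232. One-sided: 0.116.
- Pearson: X² = 42 × (3 × 21)² / (21 × 21 × 3 × 39) = 3.23, so p = 0.072 two-sided and 0.036 one-sided.
- Likelihood ratio: G = 2[3 ln(3/1.5) + 18 ln(18/19.5) + 21 ln(21/19.5)] = 4.39, so p = 0.036 two-sided.
- Yates-corrected chi-square: p = 0.231 two-sided.

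**Smallest count on varenicline that is identified against none on placebo (two-sided 0.05).**

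| Test | Split | p |
|---|---|---|
| Likelihood ratio | 3 v 0 | 0.036 |
| Pearson | 4 v 0 | 0.036 |
| Fisher | 5 v 0 | 0.048 |
| Yates | 6 v 0 | 0.027 |

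**Chance of identifying a true excess.** For each pair of assumed rates, sum Bin(a; 21, p₁) × Bin(b; 21, p₀) over all tables with a > b and two-sided p ≤ 0.05.

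| Assumed true rates | Yates | Fisher | Pearson | Likelihood ratio |
|---|---|---|---|---|
| 10% v 1% | 1.2% | 4.3% | 12.6% | 28.7% |
| 20% v 5% | 12.3% | 18.5% | 31.1% | 37.6% |
| 25% v 5% | 25.7% | 32.4% | 46.8% | 50.8% |
| 50% v 10% | 75.7% | 75.9% | 86.1% | 86.1% |

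With 19 per arm, 20% v 5% is identified 15.0% (Fisher) to 27.2% (Pearson) of the time. Read one-sided at 0.05 with 21 per arm, it is 23.7% (Fisher) to 46.0% (Pearson).

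**What an interval would show.** For 3/21 the Wilson limits are 5.0% and 34.6%; for 0/21 they are 0% and 15.5%. The Newcombe interval for the difference of 14.3 points has lower limit 0.143 − √[(0.143 − 0.050)² + 0.155²] = −0.038 and upper limit 0.143 + (0.346 − 0.143) = 0.346. That is −3.8 to +34.6 points. Even 0 v 0 leaves −15.5 to +15.5 points.

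**The case against.** The strongest reply is that the clause does not restrict reporting. A reader might infer that unflagged events will not be presented, or that a non-significant comparison will be taken as evidence of safety. The documents support neither. All events are recorded, classified and compared; identifying the significant ones comes on top of that; and nothing equates non-significance with safety. This stands.

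A reader might also infer that three cases of suicidal ideation on varenicline and none on placebo would be missed. That does not follow either. Suicidal ideation and psychosis are named reasons to stop a subject's treatment (Criteria for Intervention Discontinuation). The unblinded monitor reviews the adverse event data (General Design Issues). Serious events are reported within 24 hours (Adverse Experience Reporting) and enter the guidelines for stopping the study (Data Monitoring). The Beck scales are given at entry, week 5 and week 9 (Table 1). None of this needs a p-value. It protects subjects during the trial, but it does not settle how the arms are summarized at the end.

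It is also fair to say that any 42-subject trial is weak for rare harms, and that across these assumed rates and tests the chance of identification runs from about 1% to 86%. Both points stand. They argue against using significance as the criterion at this size, and the fix does not claim to remove the imprecision.

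The clause is directional, so a one-sided test is a possible reading. One-sided Fisher still does not identify 3 v 0, while one-sided Pearson does, so the result continues to depend on the unnamed test.

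Finally, the Aim 2 item says that for side effects "logistic regression will be performed with the treatment arm as the dichotomous outcome and the MMSE and FAB as covariates". That model has no adverse-event variable and so does not fill the gap, but its wording is a separate issue and this point does not rest on it.

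**Conclusion.** The point holds in limited form. Significance is the only stated criterion by which Aim 3 identifies an adverse event as more frequent on varenicline, and neither the test nor any estimate is specified. At 21 per arm, a 3 v 0 split is not identified by a two-sided Fisher or Pearson test and is identified by a likelihood-ratio or one-sided Pearson test. An assumed 20% v 5% excess is identified in roughly one trial in five (Fisher) to one in three (Pearson).

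These figures rest on 1:1 allocation, no loss from the safety comparison, a 0.05 level and assumed event rates. The dependence on the unnamed test for splits such as 3 v 0 needs no assumed rate. The effect is confined to the final by-arm safety summary. The primary analysis and the protection of individual subjects are untouched. This is a minor improvement worth making because it is cheap.

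**What to change.** In Outcomes and Data Analysis, side effects (Aim 3), replace the clause on significantly more frequent events with:

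> Every adverse event will be tabulated by randomized arm with number of subjects, number of events, seriousness, relatedness, and the risk difference (varenicline minus placebo) with a Newcombe 95% confidence interval; events will not be singled out, or treated as unrelated to drug, on the basis of a significance test.

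Name one interval method only. Methods can disagree about zero: for 4 v 0 the Newcombe interval is −0.2 to +40.0 points, while an exact unconditional interval is +2.0 to +40.0. The individual-subject stopping criteria and the Data Monitoring section need no change.

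The cost is one clause and a longer table. Events, seriousness and relatedness are already collected, so no new data, visits or subjects are needed. The intervals will be wide; they show the imprecision of a trial this size but do not reduce it.

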### Design and Outcomes

The design is a randomized, double-blinded, placebo-controlled study conducted at one center. The primary outcome is the change in the Berg Balance Scale. Secondary outcomes include the Activities-specific Balance Confidence Scale, Parts I-III of the MDS-UPDRS, the Timed up and go test, the Folstein Mini Mental Status Exam (MMSE), the Beck Depression Inventory, the Beck Scale for Suicidal Ideation, the Frontal Assessment Battery (FAB), and total number of falls.

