## STUDY OBJECTIVES

### Primary Objective

The hypothesis tested is that varenicline will result in improvement of balance and postural instability after eight weeks of treatment compared to placebo. The null hypothesis is that there will be no difference in tests of balance between subjects on placebo compared to those on varenicline using the Berg Balance Scale as the primary outcome. The primary and secondary outcomes will be performed by the site investigator who will be blinded to treatment.

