#### **The Berg Balance Scale**

The BBS was designed to measure changes in functional standing balance over time. This is a 14-item scale that rates each function from 0 (worst) to 4 (best). This scale measures balance abilities seen during tasks involving sitting, standing, and positional changes. Total scores are indicative of overall balance abilities, with scores interpreted in the following manner: 0 to 20, wheel-chair bound; 21 to 40, walking with assistance; and 41 to 56, independent. The BBS is relatively safe and simple to administer. It uses a quantitative scale format that has strong internal consistency and good inter- and intra-rater reliability with different patient populations, including brain injury, stroke, and geriatric patients. It has specifically been clinically validated for evaluating postural instability in PD patients.

For this study, improvement will be defined as an 8 point improvement of the scale which has been found in one study to be required to reveal a genuine change in function among older people who are dependent in activities of daily living and living in residential care facilities.

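### The 80% power rests on mislabelled inputs and on a two-group test that is not the planned primary analysis, so it is unsupported, though not shown to be too low

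*Combined protocol and SAP*

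**What the plan says.** Four parts of the combined protocol and SAP bear on this.

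- **Outcome and hypothesis.** Design and Outcomes states: "The primary outcome is the change in the Berg Balance Scale". The Primary Objective is comparative: "varenicline will result in improvement of balance and postural instability after eight weeks of treatment compared to placebo".
- **Sample size.** Outcomes and Data Analysis says "Sample size was estimated using published means and standard deviations of the BBS in PD subjects", and then "The mean of the rating scale is 40.22 with a standard deviation of 8.48". The target is introduced with "Based on a published effect size of a change of 8 points". With power 0.80 and two-sided 0.05, it arrives at 19 per group for a parallel design; 42 are recruited to cover attrition.
- **Origin of the 8 points.** The Berg Balance Scale section says "improvement will be defined as an 8 point improvement of the scale", because one study found that amount "required to reveal a genuine change in function among older people who are dependent in activities of daily living" and living in residential care. Its citation, reference 10, is by title an intrarater test-retest reliability study.
- **Primary test.** Outcomes and Data Analysis names a paired t-test on mean total BBS before and after treatment. A linear regression is added for gender, age, race and ethnicity; treatment arm is not among the variables listed.

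No SD of change, no baseline-to-follow-up correlation and no expected between-arm difference is given anywhere.

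**The concern.** A power statement describes a trial only if its difference, its SD and its test belong to the planned analysis. Here none of the three clearly does. The difference is a threshold from a reliability study in another population, yet it is labelled a published effect. The SD describes how patients' scores differ from one another, not how much a patient's score changes. The test behind the 19 is a comparison of two groups, while the named test compares before with after.

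At stake is how the result is read. Someone relying on the sample-size text would take 8 points both as an effect seen elsewhere and as the smallest difference the trial can detect. The documents support neither. A null result could then be read as excluding less, or more, than the data allow. In addition, a before-after test cannot answer the placebo-controlled question: any improvement common to both arms would count as change.

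**Working it through.** **Inputs from the documents.** Difference 8 points; SD 8.48 (reported with a mean score of 40.22); two-sided 0.05; power 0.80; 19 per group (all from Outcomes and Data Analysis).

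**Step 1: reproduce the 19.** For two groups of size n, the normal approximation is n = 2 × [8.48 × (1.960 + 0.842) / 8]² = 17.6, rounded up to 18. The exact two-sample t-test (noncentral t) gives power 0.785 at 18 per group and 0.808 at 19. So 19 is the exact answer. At 19 per group the standard error is 8.48 × √(2/19) = 2.75, and the noncentrality is 8 / 2.75 = 2.91 on 36 degrees of freedom.

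**Step 2: which test was powered?** A one-sample paired t-test with difference 8 and SD 8.48 needs 11 pairs (power 0.805). The 19 therefore comes from the two-group formula with the score-level SD, not from the named paired test.

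**Step 3: is 8.48 the SD of change?** If both visits have the same variance and correlation r, the SD of change is 8.48 × √(2(1 − r)). This equals 8.48 only when r = 0.5. The documents do not give r.

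**Step 4: a between-arm comparison adjusted for baseline.** The SD that matters is 8.48 × √(1 − r²), again assuming equal variances. At SD 8.48 and 19 per group, the difference detectable at 80% power is 7.92 points, and it scales with √(1 − r²). The values of r are assumptions.

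| r (assumed) | √(1 − r²) | Adjusted SD | Detectable difference at 80% power |
|---|---|---|---|
| 0 | 1.000 | 8.48 | 7.9 |
| 0.5 | 0.866 | 7.34 | 7.92 × 0.866 = 6.9 |
| 0.8 | 0.600 | 5.09 | 7.92 × 0.600 = 4.8 |
| 0.9 | 0.436 | 3.70 | 7.92 × 0.436 = 3.5 |

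Spending one degree of freedom on the covariate (35 in place of 36) moves 7.92 only to 7.93. Power for 8 points is thus about 0.81 at r = 0 and higher at any positive r; it is 0.90 at r = 0.5.

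**Step 5: smaller true differences.** At SD 8.48 (r = 0 in the adjusted analysis) and 19 per group, power is 0.56 for 6 points, 0.42 for 5 and 0.29 for 4.

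**The case against.** The best defence is that nothing is miscalculated, that powering on a meaningful-change value is a common and legitimate choice, and that a score-level SD is usually cautious. Much of this stands. The 19 is right for its inputs. Eight points can serve as the target difference if it is called that. For a baseline-adjusted comparison, 8.48 is the largest SD that any non-negative correlation gives, so it errs on the safe side.

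A reader might infer that the trial is underpowered for 8 points. The documents do not support that. Power for 8 points falls to 0.52 only if unadjusted change is analysed and r = 0, an extreme assumption for one scale in the same people nine weeks apart on stable medication. Even for unadjusted change, a shortfall needs r below 0.5. Nor do the documents say that a drug effect below 8 points is expected; the power figures for 4 to 6 points show what follows if it is smaller. A reader might also try to derive an SD of change from the 8 points, but the documents do not say what confidence level lies behind that threshold. That the threshold applies to individuals is itself an inference from the wording and the reference title.

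What the defence does not meet is the labelling and the test. The plan nowhere says that 8.48 was chosen as a cautious stand-in, it calls a reliability threshold a published effect, and its named test does not compare the arms.

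**Conclusion.** The concern holds as one of unsupported power, not of wrong arithmetic or proven lack of power. The 19 per group is correct for a two-sample t-test with difference 8 and SD 8.48. The 8 points is mislabelled, the SD is not that of the primary outcome, and the calculation does not match the stated paired test.

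Under the analysis that would answer the Primary Objective, the detection limit is 7.9 points at worst and possibly as low as 3.5. This rests on assumed correlations from 0 to 0.9, equal variances at both visits, an SD of 8.48 in this population and 19 evaluable subjects per group. If the correlation is low, the trial has little chance of detecting true differences of 4 to 5 points. This matters for interpretation and for the choice of primary test; it gives no reason to enrol more subjects.

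**What to change.** Keep recruitment at 42 and revise Outcomes and Data Analysis as follows.

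1. Replace the effect-size label with: *threshold for genuine change (see The Berg Balance Scale), used as the target between-arm mean difference*. State that 8.48 is a score-level SD and that the SD of change is not known.
2. Make the primary analysis the between-arm difference in week-9 BBS adjusted for baseline BBS, in place of the paired t-test. Draw the conclusion from that difference and its 95% CI.
3. Restate power for that analysis at 19 per group: detectable differences of 7.9, 6.9, 4.8 and 3.5 points at assumed r = 0, 0.5, 0.8 and 0.9. Add that at SD 8.48 (r = 0) power is 0.56, 0.42 and 0.29 for true differences of 6, 5 and 4 points.

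Optionally, tabulate by arm the proportion gaining at least 8 points, since the plan defines improvement that way but lists no analysis of it.

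**Cost.** No further subjects, visits or data: BBS is among the final-visit scales, and subjects who stop treatment are asked to return for it. The price is a change of the named primary test, which goes beyond rewording, and an open admission of limited power for effects well below 8 points if the correlation is low.

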### Data Monitoring

An independent medical monitor will be established to monitor this study. An interim safety analysis will not be performed. Guidelines for stopping the study would include new toxicological findings of varenicline or serious adverse events reported from the subjects on active medication. The independent medical monitor will meet with the PI as needed during the protocol.

### DATA COLLECTION, SITE MONITORING, AND ADVERSE EXPERIENCE REPORTING

#### Records to Be Kept

All study forms will be kept at Rush University. The records will be stored in a locked office of the site investigator. At the main site, data on the CRF will be entered into a

password-protected database. Access to the database will be restricted to the host site CRA, PI, and biostatistician.

#### Quality Assurance

The PI will meet with the study coordinator once monthly to review records, consent forms, protocol compliance, and data quality. All of the investigators will meet once every four months to review issues related to quality.

#### Adverse Experience Reporting

Adverse events will be recorded on the adverse event CRF and reported within three days. Serious adverse events will be reported within 24 hours. Detailed definitions of adverse experiences, a table for grading their severity, and details of how clinical sites are to report them, appear in the Manual of Operations.

